The evidence supporting the clinical effectiveness of traditional, CBCR is well-established and as a result, CR is a class 1 recommendation following MI, coronary artery bypass surgery, or percutaneous coronary intervention (25-29). Additionally, CR is recommended for patients who have undergone cardiac transplantation or heart valve surgery and those with chronic stable angina and stable chronic heart failure with reduced ejection fraction (30-33). Briefly, CR is associated with a 10% to 24% reduction in total mortality over 1 to 3 years and an ~ 30% decrease in re-hospitalizations over 1 year (3,4,25,34-39). We recently estimated that if CR participation was increased to 70% among eligible patients, ~25,000 lives would be saved and 180,000 hospitalizations would be prevented annually (25). In addition, quality of life and functional capacity are improved (25,39,40,83) and much of the abnormal physiology that accompanies CVD is improved [e.g., coronary artery endothelial function, autonomic function, insulin resistance] (25,41-43). Finally, mood is also favorably influenced (44,45). Taken in sum, CR is a cost effective means to deliver and advance secondary prevention to patients with known CVD via a multidisciplinary and patient-centered approach.

3.2.1. Relationship between Number of Cardiac Rehabilitation Sessions Completed and Outcomes.

Most patients attend 25 or fewer CR sessions (2-5,9), less than what is typically allowed by the majority of health insurers (e.g., Medicare allows 36 visits), potentially diminishing the functional and clinical benefits ascribed to CR. Hammill and co-workers (6) observed that a 6 session increase in number of CR sessions completed was associated with an ~ 6% decrease in risk of mortality (HR: 0.94, $p < 0.001$). Martin et al (7) reported a 1% decrease in risk for each additional CR session attended (HR: 0.99, 99% CI: 0.98-0.99). Finally, Doll et al. (8) reported a 13% reduction in risk for mortality for each increase of 5 CR sessions (HR: 0.87, 95% CI: 0.83-0.92). We previously showed, that (a) the number of sessions completed is associated with the magnitude of the increase in exercise capacity (45) and (b) higher achieved MET level at discharge from CR is related to a reduction in risk for mortality (HR: 0.60; 95% CI: 0.51-0.70) (46).

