This group of iATTEND involves a hybrid design, with the frequency of CBCR visits and HYCR visits individualized and modified based on the subject’s personal preferences and their family, transportation and work constraints. Per study eligibility criteria, patients in HYCR will engage in at least one CBCR visit. For those with no preferences as to their number of TM visits, they will be scheduled to complete 12 of their 36 visits as HYCR-TM, with the remainder being home-based without TM (up to one time per week) and/or CBCR 1 or more per week. Immediately following CR visit 1 (which will be CBCR), patient in HYCR will have the video app loaded to their smart phone or tablet (or that of a “willing to assist” family member or friend). HYCR patients receive a chest strap/wrist heart rate device to document HR before, during, and/or after exercise during the TM session. After CBCR visit 1, if the patient opts to complete the remainder of the CR session as HYCR, they will be provided with a home blood pressure unit for the regular reporting of resting blood pressure prior to each HYCR visit. HYCR subjects will be encouraged to engage in purposeful exercise ad libitum on their own each week.

Since both Blue Cross and Blue Shield of Michigan and Health Alliance Plan already cover CBCR and HYCR, only the co-payments will be covered by the project’s budget. For patients randomized to HYCR that have an insurer that does not yet cover CR delivered using TM (e.g., Medicare), their CR visits will be covered by the project’s budget. For all patients randomized to CBCR, their co-payments will be covered by the project’s budget.

Program education for patients in HYCR will be delivered using the twenty-eight, 7-15 min audio PDF’s that are free to access from the Health System’s web site. For patients in the HYCR group, 1-3 of the audio PDF’s will be “assigned” (based on their ITP) for viewing before their next CR visit, with content discussed with the appropriate CR staff person during their next remote or center-based visit.

The following table (Table 3) provides a descriptive summary of the CR protocol for subjects in the two study groups of iATTEND.

Table 3. Summary of the CR protocol for subjects in the two study groups of iATTEND.

	Hybrid CR	Center-Based CR
Staff : Subject ratio (contact time, setting)	1:1 (12 to 15 min, individual setting)	4:1 (60 min, group setting)

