10.1. Randomization Procedure

Using computer generated randomization, the randomization process will be stratified by race and sex and blocked to ensure balance at random accrual points. Lists were compiled for the 4 sex-race specific strata. As new participants are added to the study they will be assigned the next available treatment assignment (CBCR, HYCR) based on the lists provided. The project manager will be responsible for treatment assignment as all other staff involved in the study will be blinded as to the randomization lists to avoid bias.

10.2. Sample size and power calculations.

We propose to enroll a total of 270 patients evenly randomized into two groups of 135 patients each. To determine power for **Hypothesis 1**, we will use a Student's t-test approach. From recent data from our administrative CR data base, we believe that the CBCR group will complete 21 ± 13 (mean + sd) visits over the course of the study. The test, with a two-sided 0.05 alpha level, will have 80% power to detect an increase of 4.5 visits. We believe this to be a clinically significant difference (5).

Also, for **Hypothesis 2**, our recent administrative data indicates that 24% of patients in our CBCR program complete 36 visits. A chi-squared test with a two-sided 0.05 alpha rate and 135 subjects per group will have 80% power to detect an **increase to 39.8% or more in the HYCR group** (effect size=15.8 percentage point increase).

Hypothesis 3, 4 and 5 require longitudinal measures six months after CR is completed, so it is possible that some lost to follow-up will occur at follow-up testing point number 2. If we assume that no more than 20% will be lost, our sample size for this analysis will be at least 108. We anticipate a standard deviation of the change in meters walked in the 6-minute walk to be 107 meters (based on data from the Henry Ford Core Exercise Laboratory) When the sample size in each group is 108, a two group 0.05 one-sided t-test will have in excess of 90% power to reject the null hypothesis that the CBCR and HYCR groups are not equivalent (the difference in means is 50 meters or farther), in favor of the alternative hypothesis that the means in the two groups are equivalent.

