The measured of peak VO₂ should have a standard deviation near 6 (86). With a sample size of 108 per group, a two-group one-sided t-test will have greater than 80% power to reject the null hypothesis that the CBCR and HYCR groups are not equivalent (the difference in means is 2.0 mL/kg/min or farther), in favor of the alternative hypothesis that the means in the two groups are equivalent.

Based on Campbell, et al. (87), we anticipate that the standard deviation of the Short Form Health Survey (SF-12) physical component summary will be 22 and the mental component summary will be 18. When the sample size in each group is 108, a two-group 0.05 one-sided t-test of the physical component scale will have 80% power to reject the null hypothesis that the

CBCR and HYCR are not equivalent (the difference in means is 7.5 or further from zero in the same direction), in favor of the alternative hypothesis that the means of the two groups are equivalent. The power for the mental component summary will exceed 90%.

10.3. Data Analysis Plan.

Data analysis will begin with preparatory activities such as checking for complete data entry, identification of outliers, and other such data cleaning tasks. Once the above tasks are completed, the data base will be “locked” for analyses. The Statistical Analysis System, (SAS, version 9.4) will be used for data analysis. A detailed descriptive analysis of all quantitative data will be performed involving the summarization of data and the use of inferential and graphical exploratory analytic techniques. The information obtained from this preliminary investigation will be used to: 1) describe univariate and bivariate sample distributions of the data; 2) identify the interrelationships between variables (i.e., need for covariate adjustment); and 3) check for violations of assumptions underlying identified statistical techniques (e.g. independence, linearity, homoscedasticity, normality). In the event that statistical assumptions are severely violated, data transformations or nonparametric methods will be employed. An intention to treat approach will be utilized for all analyses. For hypothesis 1 the number of visits completed before lost to follow up will be used and for hypothesis 2 a yes/no response will be generated based on the observed data.

R33- Primary Aim: Assess the effect of a HYCR program on over-all patient attendance

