For the **Primary Hypothesis** (number of sessions completed), if the distribution of the number of sessions completed is normal then a Student’s t-test will be used for comparison of the two groups. In the likely event it is skewed a two-sample Wilcoxon with a Fligner-Policello correction for unequal variances will be used. **Hypothesis 2** (percentage of patients completing 36 CR sessions) will be addressed using a Chi-squared test for comparison of proportions.

R33- Secondary Aim: Assess the effect of HYCR on exercise capacity and quality of life.

Hypotheses 3 and 4 (both address measures of exercise capacity) and **Hypothesis 5** (QOL) all involve assessing if the two group responses are equivalent. A two one-sided test approach will be used to demonstrate equivalence between the two groups.

There are several identified **exploratory aims** for this project, including but not limited to:

- (a) short-term (6 month) retention of CR-related outcomes [e.g., exercise capacity, QOL, and self-engaged (not CR) purposeful exercise and total physical activity habits]
- (b) program cost effectiveness.

Analyses of the exploratory aim associated with the short-term retention of CR-related outcomes will be analogous to the analyses described above, such that Student's t-test, Chi-squared tests or their nonparametric alternatives will be utilized.

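### Intention to treat is the only analysis planned for the H3–H5 equivalence tests; one pre-specified supportive analysis by program received would show whether a hybrid shortfall is being diluted into the margin

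*Combined protocol and SAP*

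**What the plan says.** The Data Analysis Plan (10.3) sets one analysis principle: "An intention to treat approach will be utilized for all analyses". For H3–H5 the same section says: "A two one-sided test approach will be used to demonstrate equivalence between the two groups". It defines no received-program, minimum-sessions or attendance-adjusted analysis for these hypotheses.

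Section 2.2 frames H3–H5 as comparisons of patients by randomized group. Section 10.2 sizes H3 with "a two group 0.05 one-sided t-test will have in excess of 90% power" at 108 per group, a margin described as "the difference in means is 50 meters or farther", and this variability: "We anticipate a standard deviation of the change in meters walked in the 6-minute walk to be 107 meters". For peak VO2 it uses an SD of 6 and a margin of 2.0 mL/kg/min.

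On attendance, 10.2 says "we believe that the CBCR group will complete 21 ± 13 (mean + sd) visits over the course of the study", and that 24% of the site's CBCR patients complete all 36 visits. On dose, 3.2.1 reports that "the number of sessions completed is associated with the magnitude of the increase in exercise capacity". Patients who stop, or are administratively dropped from rehabilitation, are still scheduled for both follow-up tests (4.3.5.a, 4.6), so their results enter the comparison.

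**The concern.** For H1 and H2, which aim to show a difference in attendance, intention to treat is the natural choice. For H3–H5 the aim is to show that no important difference exists. There, anything that leaves patients in both arms with only part of their program can move a real difference toward zero, and so toward the claim.

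The plan itself supplies the ingredients: partial attendance is expected, gains are said to follow sessions completed, and poor attenders are still tested.

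What is at stake is how a positive result will be read. Section 3.3 says rehabilitation programs considering a hybrid model need assurance that outcomes match those of CBCR. A result inside the margin could mean that the hybrid program works as well, or that too little of either program was taken for a shortfall to show. The intention-to-treat test alone does not distinguish the two.

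**Working it through.** **Inputs.** From 10.2: n = 108 per arm (135 less 20%); six-minute walk SD 107 m and margin M = 50 m; peak VO2 SD 6 and margin 2.0; one-sided alpha 0.05; CBCR attendance 21 of 36; detectable attendance gain 4.5 visits. The documents give no dose-response slope, so linear scaling is an assumption.

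**Formulas (normal approximation).** SE = SD × √(2/n). The probability that TOST declares equivalence at a true difference d is Φ((M − d)/SE − 1.645) + Φ((M + d)/SE − 1.645) − 1.

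**Step 1: the plan's own figure.** Six-minute walk: SE = 107 × √(2/108) = 14.56 m. A single one-sided test gives Φ(50/14.56 − 1.645) = Φ(1.79) = 96.3%, and TOST at d = 0 gives 92.6%. The stated power above 90% is reproduced either way. For peak VO2, SE = 0.816; the one-sided figure is 78.9% and TOST gives 57.9%, against a stated power above 80%. That gap is a separate matter.

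**Step 2: dilution with equal attendance.** Let HYCR be worse by exactly the margin at full attendance, and let the difference scale with the fraction of sessions attended. At 21/36 = 58.3%:

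- Six-minute walk: d = 50 × 21/36 = 29.2 m. Probability = Φ(20.83/14.56 − 1.645) + Φ(79.17/14.56 − 1.645) − 1 = 0.415.
- Peak VO2: d = 2.0 × 21/36 = 1.17. Probability = Φ(0.833/0.816 − 1.645) + Φ(3.167/0.816 − 1.645) − 1 = 0.253.

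The range over assumed attendance is:

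| Sessions attended | Six-minute walk | Peak VO2 |
|---|---|---|
| 100% | 5% | 5% |
| 75% | 22% | 15% |
| 58% (21 of 36) | 41% | 25% |
| 40% | 66% | 39% |
| 0% | 93% | 58% |

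**Step 3: unequal attendance.** Let HYCR attend 21 + 4.5 = 25.5 sessions and CBCR 21. Let G be the assumed CBCR gain at full attendance and S the HYCR shortfall at full attendance. Then d = (21/36)G − (25.5/36)(G − S).

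- S = 50 m, with G = 50, 100, 150 m: d = 29.2, 22.9, 16.7 m; equivalence is declared 41%, 59%, 74% of the time.
- S = 0, same G: d = −6.3, −12.5, −18.8 m (HYCR better); equivalence is declared 90%, 82%, 69% of the time, against 93% at d = 0.

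So a true HYCR shortfall is masked in both settings. If the models are equally effective and HYCR attends more, the difference moves away from zero and equivalence becomes harder to show.

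**Step 4: what a smaller supportive set can do.** Retention in such a set is not given. Assuming 50% to 80% of 108 (54 to 86 per arm), TOST power at a true difference of zero is 57% to 84% for the walk and 7% to 41% for peak VO2.

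**H5.** Section 2.2 names the Dartmouth COOP, while the margin and SDs in 10.2 are for the SF-12, and the documents give no dose-response for quality of life. The effect on H5 as named cannot be computed.

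**The case against.** The strongest objection is that intention to treat answers the question the protocol asks. Section 2.2 compares patients as randomized, the trial is one of effectiveness, and attendance is its primary endpoint and part of the strategy under test. A reader might infer from the table that poor attendance raises the false-positive rate from 5% to 41%. The documents do not support that. In the illustration the as-randomized difference is 29 m, inside the 50 m margin, so declaring equivalence of assignment is correct. The 5% row belongs to a different question, the effect at full attendance, which the protocol does not pose. This objection stands in full and decides which test is the main one.

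The size is also open to challenge. It needs a full-margin shortfall, a linear dose-response and equal attendance. The last runs against the primary hypothesis that HYCR attends more. Missed sessions are also not zero exercise, since both arms are encouraged to exercise on their own. This stands as well: the numbers show a mechanism and do not forecast a result.

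A reader might go further and treat 12 of 36 visits as the whole contrast between the arms, because 4.3.5.b says of patients without a preference that "they will be scheduled to complete 12 of their 36 visits as HYCR-TM". That does not follow. The same section lets the other visits be home-based without telemedicine, at the center, or both, whereas Table 3 caps center sessions at 12. The two places conflict and must be reconciled. A planned mix of sites is in any case the assigned hybrid program.

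Finally, sessions by arm will be reported as the primary result, and reasons for stopping will be collected (10.3). Readers will therefore see whether attendance was low. They will not see whether outcomes differ among those who took the program, so this answers the concern only in part.

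**Conclusion.** This is a worthwhile, inexpensive improvement; the main test is not in error. Intention to treat is the only analysis stated for H3–H5, and it is valid for equivalence of assignment. Read alone, it cannot support the further statement that the hybrid program, as received, works as well as the center program.

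Under linear dose-response, equal attendance at 21 of 36 and a full-margin shortfall, equivalence of assignment would be declared about 41% of the time on the walk and 25% on peak VO2. These figures are illustrative. The plan supports the direction of the dose-response for exercise capacity but not its slope, and supports neither for quality of life. The masking applies to a true HYCR shortfall, the direction that matters for the non-inferiority wording in 2.2. It is not a general pull of the arms toward each other.

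**What to change.** Keep intention to treat as the main test for H3–H5, and unchanged for H1 and H2. Add to 10.3:

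1. One supportive analysis of H3–H5 in patients who received their assigned program, with the same minimum-sessions rule in both arms: for example, at least 18 of 36 sessions of any type the assigned program allows. Adjust for baseline value, race and sex (the last two are the randomization strata). Fix the set before outcomes are seen.
2. Report its 90% confidence interval beside the intention-to-treat interval and attendance by arm.
3. Word the main conclusion as equivalence of being assigned to HYCR. Extend it to the program as received only where the supportive estimate is consistent, and state beforehand how consistency will be judged.

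Do not add a rule that automatically withdraws the claim when the supportive interval crosses the margin. At an assumed 54 per arm, truly equivalent programs would pass only 57% of the time on the walk and about 7% on peak VO2. Do not set a HYCR-specific criterion, such as a minimum of remote sessions, until 4.3.5.b and Table 3 have been reconciled.

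The cost is one analysis from data already collected and a few lines of SAP text, with no change to sample size or visits. The downside is that the supportive set is smaller and not protected by randomization, because attendance is the primary outcome and may differ by arm. Patients in it may also have attended anywhere from 18 to 36 sessions, so it reduces dilution without removing it. It serves as a consistency check only.

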3.1. Secondary Prevention in Vulnerable, at Risk Patients with Cardiovascular Disease

Patients of lower socio-economic status (SES) experience a disparate or disproportionate level of morbidity and recurrent events following an initial heart problem, a portion of which can be explained by poorer engagement in secondary preventive strategies (e.g., cigarette cessation, blood pressure and lipid control, physical activity, and compliance to prescribed medication) (1,10,20,23,24). Additionally, following a cardiac event annual mortality is lower among Caucasians versus others (4,6).

Much of the research to date that pertains to CR has involved patients that were healthier and socially and financially better able to adhere to CR and; therefore, able to participate in CR-related research. Limited prior research suggests lower participation rates and fewer CR sessions completed among minorities and people of lower SES (3,9). The cardiovascular health care needs of these patients are real (and grossly understudied). Advancing and evaluating CR and its associated secondary prevention strategies (17,18) in a predominately urban, vulnerable cohort of at-risk patients represents an ideal opportunity to potentially impact their health care outcomes ... and is worthy of further investigation (3).

3.2. Cardiac Rehabilitation as a Secondary Prevention Therapy... Role and Clinical Effectiveness

Today, more so than ever before, the majority of CR programs in the US no longer represent an “exercise-only” intervention. CR is now a multidisciplinary and multifaceted secondary prevention service that addresses the core components of CR as defined by the AHA, AACVPR and ACC (17,18). Therefore, the deliverables from CR should be the same, regardless

if provided in center-based CBCR or a combination of CBCR and remote-/home-based CR (“hybrid” CR, HYCR).

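### H1 and H2 are tested without the race-by-sex randomization strata; if race or sex predicts attendance, both tests stay valid but are slightly conservative

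*Combined protocol and SAP*

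**What the plan says.** **Allocation.** Section 10.1 says randomization is "stratified by race and sex and blocked to ensure balance at random accrual points", with a separate list for each of four sex-race strata. Section 4.3.4 agrees.

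**Tests.** Section 10.3 compares sessions completed (H1) by Student's t-test if the distribution is normal. If it is skewed, which the plan expects, it uses a two-sample Wilcoxon test with a Fligner-Policello correction for unequal variances. H2 "will be addressed using a Chi-squared test for comparison of proportions". No test contains the strata, and no confidence interval is named for either hypothesis.

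**Sample size.** Section 10.2 sizes the trial on the same unstratified tests. For H1 it expects that "the CBCR group will complete 21 ± 13 (mean + sd) visits over the course of the study" and states: "The test, with a two-sided 0.05 alpha level, will have 80% power to detect an increase of 4.5 visits".

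**Adjustment.** The only mention is in the opening paragraph of section 10.3. Exploration after database lock is to show, among other things, whether covariates need adjusting for. It names no covariate, no model and no hypothesis.

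**Prognosis.** The overview (section 1) says African Americans are less likely to attend. Section 3.1 refers to limited earlier research suggesting "fewer CR sessions completed among minorities and people of lower SES". Neither gives a size, and neither speaks to sex.

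**Status of H2.** It sits under the primary aim in section 2.1 but is the first secondary endpoint in section 5.2.

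**The concern.** Blocking within strata keeps the arms nearly balanced on race and sex, so chance imbalance on those factors contributes almost nothing to the true sampling variance of the arm difference. An unstratified test still estimates its standard error from the total variance, including the part between strata. If the strata predict the outcome, that standard error is too large, the true type I error falls below 5%, and the precision that the stratified design could give is not used.

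The second point does not depend on effect size. Because the strata are absent from the named tests and adjustment is left open, whether to adjust H1 or H2 would be decided after lock. Section 7.3 says that the analysing biostatistician holds the treatment codes. Race and sex were chosen in advance and define the randomization, so nothing has to be learned from the data before fixing their role.

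**Working it through.** **Inputs from section 10.2.** "We propose to enroll a total of 270 patients evenly randomized into two groups of 135 patients each"; SD 13 sessions; target difference 4.5 sessions; two-sided alpha 0.05. For H2, "our recent administrative data indicates that 24% of patients in our CBCR program complete 36 visits", against 39.8% in the hybrid arm.

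**Input from section 3.5.** About 80% of the site's CR patients are African American.

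**Assumed.** R2, the share of outcome variance explained by the four strata. The documents do not give it, so a range is shown.

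**Step 1: reproduce the plan.**
- H1: SE = 13 × √(2/135) = 1.582. Power = Φ(4.5/1.582 − 1.96) = Φ(0.884) = 81.2% (80.9% by noncentral t). The stated 80% reproduces.
- H2: the pooled proportion is (0.24 + 0.398)/2 = 0.319. SE under the null = √(2 × 0.319 × 0.681/135) = 0.0567. SE under the alternative = √((0.24 × 0.76 + 0.398 × 0.602)/135) = 0.0559. Power = Φ((0.158 − 1.96 × 0.0567)/0.0559) = 79.9%. The stated 80% reproduces.

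**Step 2: H1 under stratified blocks.** The true SE is 1.582 × √(1 − R2), but the unstratified test still uses 1.582. Hence:
- SE excess = 1/√(1 − R2) − 1
- actual alpha of the unstratified test = 2 × (1 − Φ(1.96/√(1 − R2)))
- unstratified power = Φ((4.5 − 1.96 × 1.582)/(1.582 × √(1 − R2)))
- stratified power = Φ(4.5/(1.582 × √(1 − R2)) − 1.96)

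| Assumed R2 | SE excess | Actual alpha | Power, unstratified | Power, stratified |
|---|---|---|---|---|
| 0 | 0 | 5.0% | 81.2% | 81.2% |
| 2% | 1.0% | 4.8% | 81.4% | 81.9% |
| 5% | 2.6% | 4.4% | 81.8% | 83.1% |
| 10% | 5.4% | 3.9% | 82.4% | 85.0% |

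**Step 3: H2, same scaling on the risk difference.** For R2 of 0 / 2% / 5% / 10%, power is 79.9% / 80.1% / 80.5% / 81.1% unstratified against 79.9% / 80.7% / 81.9% / 83.9% stratified.

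**Step 4: which R2 is realistic?** With 80% African American patients, a race gap of d sessions gives R2 = 0.8 × 0.2 × d²/13² = 0.16 d²/169. Race alone therefore needs d = √(0.02 × 169/0.16) = 4.6 sessions for R2 of 2%, 7.3 for 5% and 10.3 for 10%. The expected center-based mean is 21 and the target effect 4.5, so 10% is an outer bound and 0 to 5% the more realistic range. Adding a sex gap, with 35% women assumed, gaps of 4 (race) and 2 (sex) sessions give R2 of about 2%; gaps of 6 and 4 give about 5.6%.

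**Step 5: simulation.** Stratified blocks, a normal outcome and 6,000 runs per scenario (Monte Carlo error about 0.5 points for power) gave, unstratified against stratum-adjusted:
- H1: 80.4% against 80.9% for gaps of 4 and 2 sessions; 81.0% against 82.3% for gaps of 6 and 4.
- H2, chi-squared against Cochran-Mantel-Haenszel: 80.5% against 80.6% for completion gaps of 10 (race) and 5 (sex) percentage points; 80.4% against 81.2% for gaps of 15 and 10.

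**Limits.** The H1 figures are normal-theory results, while sessions have a target of 36 and the plan expects skew. The Wilcoxon/Fligner-Policello case was not computed.

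**The case against.** **The loss is conditional and may be nil.** This stands. Section 3.1 is hedged, no size is given for race, and nothing cited concerns sex. Several design features could also narrow a race gap: patients must have agreed to CR and have device and equipment access (4.3.1.a), the project pays co-payments and uninsured sessions (4.3.5.a), and transport and other barriers are addressed in both arms (4.5.2).

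**No planned power is lost.** This stands too. A reader might infer that the primary test is invalid or the trial underpowered. The documents do not support that: both stated powers reproduce without strata, and alpha is at or below 5%.

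**The plan already contemplates covariate adjustment.** This does not answer the point. The wording in section 10.3 fixes neither covariates nor method and leaves the decision until after lock.

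**The change is not free of side effects.** This stands in part. The plan chose Fligner-Policello to guard against unequal variances. A plain stratified Wilcoxon test would drop that protection, and a linear model would compare means instead of ranks. The non-African-American strata are also small: about 20% of 270 is 54 patients across two strata, and with 35% women (assumed) the smallest stratum is 0.20 × 0.35 × 270, about 19 patients. That is workable, but it calls for a rule on sparse strata.

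**Conclusion.** The mismatch between design and analysis is real: allocation uses four strata, and the named H1 and H2 tests use none. Its effect on the error rate is in the safe direction. For R2 between 0 and 5%, the unstratified H1 test forgoes 0 to about 1.3 power points (83.1 − 81.8) and carries a standard error up to 2.6% too large; at R2 of 10% the figures are about 2.6 points and 5.4%. The loss is nil if neither race nor sex predicts attendance. All of this rests on an assumed R2 and normal-theory formulas.

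Two stronger readings should be avoided. The documents do not establish that the primary standard error is in fact too large, because they give no prognostic strength. Nor does the point apply to two primary endpoints: H1 is primary, while H2 is a listed secondary endpoint. This is an inexpensive improvement in precision and pre-specification, and it does not threaten the trial's conclusion.

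**What to change.** Pre-specify the randomization strata in section 10.3 for both hypotheses.

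- **H1.** Use a linear model of sessions on arm plus the four race-by-sex strata, with heteroscedasticity-robust standard errors. If a rank test is preferred, use a stratum-combined rank test whose variance estimate keeps the unequal-variance protection, for example a Fligner-Policello-type variance computed within each stratum and then combined. Choose one before unblinded data are seen.
- **H2 (secondary endpoint).** Use a Cochran-Mantel-Haenszel test over the four strata, with a stratum-weighted risk difference and its 95% confidence interval.
- **Sparse strata.** State in advance when strata are pooled and in what order.
- **Other covariates.** State that the strata are the only adjustment in the main H1 and H2 analyses, and that anything prompted by the exploratory work is supplementary.

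The cost is about one sentence per hypothesis plus the pooling rule. It needs no new data and no change to sample size. The one real trade-off is that the linear model for H1 answers a question about means, not ranks.
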